The analysis plan for frequency and severity of seizures (secondary outcome measures) assessed the pattern of change over time relative to baseline. The non-parametric Friedman's test was used since seizure frequency and severity outcome measures were not normally distributed. Wilcoxon's signed rank test with Bonferroni's multiple comparison correction was utilized as a post-hoc analysis for pairwise comparisons between baseline and each post-baseline time point.

Further parametric analysis used the generalized least squares statistical techniques for modeling longitudinal data, an extension of mixed effects models that accommodates heteroscedacity and correlation within group errors (Pinheiro and Bates, 2000), after normality of outcome measures were achieved through log-transformation methods. The longitudinal analysis included each month following baseline up to the 12-month endpoint, with a log transformation of seizure measures regressed on time (months), gender, and several identified baseline clinical variables including number of AEDs, number of AEDs tried, and history of epileptic surgery. A cubic spline with 4 knots (carefully chosen with AIC and BIC) was put on time to capture the non-linear trend in seizure outcome measures. AIC and BIC also aided in the choice of the specified correlation structure for this analysis.

Effectiveness of CBD exposure on the population of interest was established with contrast estimates of percentage reduction in seizure outcome measures at each post-baseline time point relative to baseline from model.

Both parametric and non-parametric methods were repeated using last observation carried forward (LOCF) principle on the data instead of complete cases of the data. An alpha level of 5% was used to achieve statistical significance.

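### The SAP states no multiplicity control, key month or overall test for the monthly model contrasts said to establish effectiveness, although it Bonferroni-corrects the parallel Wilcoxon comparisons

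*SAP*

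**What the plan says.** All the relevant text is in the SAP's description of the secondary seizure analyses.

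- **Non-parametric analysis.** An omnibus test comes first: "The non-parametric Friedman's test was used since seizure frequency and severity outcome measures were not normally distributed". Then "Wilcoxon's signed rank test with Bonferroni's multiple comparison correction was utilized as a post-hoc analysis for pairwise comparisons" of baseline with each later time point. The number of time points is not given.
- **Model analysis.** A generalized least squares model is fitted to log-transformed seizure measures. "The longitudinal analysis included each month following baseline up to the 12-month endpoint", and "A cubic spline with 4 knots (carefully chosen with AIC and BIC) was put on time". The correlation structure was also chosen with AIC and BIC.
- **Conclusion.** Effectiveness is said to have been established with "contrast estimates of percentage reduction in seizure outcome measures at each post-baseline time point relative to baseline from model".
- **Error rate.** After saying that both sets of methods were repeated with LOCF, the SAP closes: "An alpha level of 5% was used to achieve statistical significance".

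For the model contrasts the SAP gives no adjustment, simultaneous interval, key month, overall test of the time term or success rule. Seizure frequency and severity are secondary outcomes, and the SAP describes the plan as focused on safety. The protocol's Data Analysis section calls the study observational and says power is not a relevant parameter.

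**The concern.** Both analyses compare baseline with a series of later time points for the same outcomes in the same children. The non-parametric one has an omnibus test followed by a familywise correction. The model-based one has neither in the text, yet it is the one the SAP ties to effectiveness.

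A reader therefore cannot tell what error rate the effectiveness statement carries. If significance in any single month is enough, twelve looks at 5% give more than a 5% chance of a false finding. A month significant in the model but not in the corrected Wilcoxon analysis could differ only because the two are held to different thresholds.

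**Working it through.** **The plan's own figures.** The documents state no familywise error rate for the seizure analyses. Their only design calculation is the 90% confidence interval half-width at n = 100 in the protocol's Data Analysis section. It reproduces: 1.645 × √(0.10 × 0.90 / 100) = 0.049, and 1.645 / √100 = 0.164 SD. It does not bear on this point.

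**Inputs from the SAP.** Alpha 5%; contrasts of each month with baseline up to month 12; cubic spline with 4 knots on time; two outcomes.

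**Assumptions, because the SAP is silent.**
- 12 contrasts per outcome (months 1-12), with baseline as month 0 of the fitted curve.
- Two-sided tests, large-sample normal theory, complete data.
- Spline type: either restricted cubic with 4 knots (3 df for time) or unrestricted cubic with 4 interior knots (7 df).
- Error correlation: compound symmetry 0.6, AR(1) 0.5 or AR(1) 0.8.

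**Simple bounds.** For 12 tests the Bonferroni upper bound is 12 × 0.05 = 0.60. Independence would give 1 − 0.95^12 = 0.46. Neither is realistic, because all contrasts share one baseline and one smooth curve.

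**Correlated calculation.** Let X be the spline basis at months 0-12 and V the error correlation matrix. The coefficient covariance is proportional to C = (X′V⁻¹X)⁻¹. With contrast rows L_m = x_m − x_0, the contrasts have covariance LCL′. Scaling this to a correlation matrix R, I drew Z ~ N(0, R) 400,000 times under no change and computed:
- any significant month: P(max |Z_m| > 1.96)
- any false reduction: P(min Z_m < −1.96)
- simultaneous 95% critical value: the 95th percentile of max |Z_m|

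| Time term | Correlation | Any month | False reduction | Critical value | Ratio to 1.96 |
|---|---|---|---|---|---|
| Restricted, 4 knots | CS 0.6 | 0.134 | 0.067 | 2.39 | 1.22 |
| Restricted, 4 knots | AR(1) 0.5 | 0.139 | 0.070 | 2.41 | 1.23 |
| Restricted, 4 knots | AR(1) 0.8 | 0.134 | 0.067 | 2.39 | 1.22 |
| 4 interior knots | CS 0.6 | 0.228 | 0.114 | 2.63 | 1.34 |
| 4 interior knots | AR(1) 0.5 | 0.238 | 0.118 | 2.64 | 1.35 |
| 4 interior knots | AR(1) 0.8 | 0.214 | 0.107 | 2.59 | 1.32 |

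The nominal rate is 5% for either direction and 2.5% for a reduction. A wider grid (AR(1) 0 to 0.9, compound symmetry 0.5) gave 13-14% and 20-24% for any month, with critical values 2.37-2.41 and 2.57-2.66.

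**Other decision rules, same draws.** Requiring a significant reduction in at least 6 of 12 months gives 1-2% error, and requiring all 12 gives under 0.3%. Testing month 12 alone gives 5% two-sided.

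**Bonferroni on the contrasts.** At 0.05/12 = 0.0042 each (|z| > 2.87), the familywise error would be about 1.4% (restricted) or 2.3-2.7% (interior knots). That controls the error but is wasteful for correlated contrasts.

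**Holm against Bonferroni.** Bonferroni compares every p-value with 0.05/k. Holm compares the ordered p-values with 0.05/k, 0.05/(k − 1), …, 0.05, stopping at the first failure. Its thresholds are never smaller, so it rejects at least as often with the same familywise control.

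**The case against.** The strongest reply is that the SAP never says the contrasts were tested one by one at an uncorrected 5%. It speaks of contrast estimates and gives one alpha for everything. This stands: absence of correction is inferred from silence, and the finding is that no correction is stated.

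A reader might go further and infer that the effectiveness claim rests on an inflated error rate. The documents do not support that, because they contain no rule that any single significant month suffices. Under a fixed-month or most-months rule the inflation disappears, as shown above. What remains is that no rule is given, so the any-month reading is left open.

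Two other enlargements are tempting. One is to compound the error over frequency and severity as if they were independent; they are measured in the same children and the documents give no basis for independence. The other is to count the LOCF repeat as a second family; the SAP presents it as a repeat of the same analyses, not as a separate chance of success.

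The two analyses are also not identical. One is a rank test on observed data, the other a contrast from an adjusted log-scale curve. The SAP gives no number of time points for the Wilcoxon tests, so they need not be the same 12 months. They remain parallel in purpose, and estimates and raw p-values can still be compared. Bonferroni for the Wilcoxon tests is valid, so moving to Holm is a gain in efficiency and not the correction of an error.

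Finally, the model is introduced as a further analysis of secondary outcomes. This lowers the priority, but secondary status did not stop the SAP from correcting the Wilcoxon tests.

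**Conclusion.** The point holds as a gap in the stated error control. The SAP protects the Wilcoxon comparisons by name and states no protection for the model contrasts to which it ties effectiveness.

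The size is conditional. If 12 contrasts per outcome are each read at two-sided 5% and any month counts, the chance of a false significant month is about 13-14% or 21-24% per outcome, depending on the spline. For a false reduction it is about 7% or 11-12%, against 2.5%. These figures rest on the assumed number of contrasts, spline type and error correlation. They take no account of knots and correlation structure having been chosen with AIC and BIC. Modest priority is appropriate for secondary outcomes in a single-arm study focused on safety.

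**What to change.** State one of the following for the model contrasts, separately for seizure frequency and severity:

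1. Report all monthly contrasts with simultaneous 95% intervals by the single-step max-t method, using the joint covariance of the fitted contrasts. The critical value would be about 2.4-2.65 in place of 1.96 under the settings above; the actual value comes from the fitted model.
2. Name the month-12 contrast as the only one tested, at 5%, and label the other months descriptive, with pointwise intervals identified as such.

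In either case say what finding counts as effectiveness. For the Wilcoxon tests, replace Bonferroni by Holm and give the number of comparisons.

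The cost is SAP wording, plus one post-processing step on the fitted model under option 1, with intervals about 22-35% wider. Option 2 costs only wording and gives up formal claims for the other months. Holm costs nothing in error control. No new data are needed.
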